To assess the potential for telerehabilitation to enhance visual function by providing remotely-delivered LVR training to use magnification devices (i.e., hand-held or stand optical magnifiers, electronic magnifiers). Following basic LVR (i.e., one in-office training session) for new magnification device(s), we aim to determine if there is additional gain in visual functioning by randomizing subjects (2:1) to telerehabilitation or additional in-office LVR (active control). This will help provide estimates of effect size to plan a future larger-scale randomized controlled trial. We will compare visual function changes with the Activity Inventory questionnaire and validated reading tests in 60 LV patients with central vision loss due to any ocular disease recruited from 10 centers. Participants will be assessed before and after two consecutive periods: (1) no further training will be provided for one month after a single LVR training session (i.e., basic LVR), followed by (2) up to three LVR sessions over a three month period either via telerehabilitation (n=40) in the participants' homes with study loaner equipment (iPad/smartphone, stand, reading cards) via remote control assistance, or in-office LVR (active control; n=20). Multiple sessions will be conducted if the LVR provider deems the participant is not completely proficient with their magnification device. We will determine which patient characteristics and/or magnification devices are most likely to benefit from telerehabilitation, to be targeted in a future, larger-scale, phase III trial.

The primary goal of this proposal is to refine the methods and procedures for implementing these innovative technologies for LVR, in order to develop future protocols for randomized controlled trials. In the future, we envision that telerehabilitation could improve efficiency and patient outcomes by changing the method by which follow-up LVR services are provided. This is a high priority given the increasing prevalence of LV, paucity of LVR providers, and barriers related to transportation and geography.

Background and Significance: Provide a summary of the background for this study and explain how it will contribute to existing knowledge.

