Multiple regression analyses will assess if effect sizes for the telerehabilitation and in-office LVR control group (i.e., changes in the outcomes: Activity Inventory score, reading speed) are related to the number of telerehabilitation sessions, patient demographics, visual acuity, contrast sensitivity, diagnosis, or scores on the SF36, Telephone Interview for Cognitive Status (TICS), Geriatric Depression Scale, or Hospital Anxiety Depression Scale questionnaires. We will apply advanced statistical methods (e.g., multilevel models) for missing data. We will perform a Rasch analysis of our Activity Inventory data in comparison to a very large database of LV patients (several thousand) who have completed the Activity Inventory. Goals and activities have their item measures, and the fit properties of the Activity Inventory from the database of previous responses can be used to convert raw scores into person measures. In the event of non-normally distributed data, we will use a binary outcome (proportion of subjects with improvement greater than 0.14 logits) to compare changes between telerehabilitation and in-office LVR for the Activity Inventory domains using chi-square tests and logistic regressions.

Sample Size calculation: We plan to enroll and compare findings for two equal sized groups based on visual acuity (VA); i.e., those better or worse than 20/63. A sample size calculation for matched pairs t-test revealed that 18 subjects in each of the 2 groups would detect a within-subject mean improvement of 0.14 logits on the Activity Inventory (primary outcome) following telerehabilitation (equivalent to 1-line or 0.1 logMAR VA), when considering a standard deviation of 0.17 logits for the differences, power of 0.80 and 0.05 type I error probability. We will aim to enroll a total of ~40 subjects randomized to telerehabilitation (given our 2:1 randomization plan), and aim to have a total of ~20 active controls randomized to receive in-office LVR. We will determine the effect sizes for basic LVR (one session in-office as part of standard of care), telerehabilitation and additional in-office LVR for changes in the Activity Inventory and reading outcomes.

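### The only powered analysis is an uncontrolled within-person change after telerehabilitation with no stated interval; the randomised difference from in-office LVR should be the main effect estimate

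*Combined protocol and SAP*

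**What the plan says.** Specific Aims sets out to learn, by 2:1 randomisation to telerehabilitation or further in-office LVR, whether there is gain beyond basic LVR. It adds: "This will help provide estimates of effect size to plan a future larger-scale randomized controlled trial". Participants are assessed around two consecutive periods. In the first, "no further training will be provided for one month after a single LVR training session". In the second, lasting three months, both arms receive up to three sessions. Under Outcome measures, the Activity Inventory is given at study entry, one month and four months.

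The Sample Size calculation does not use the randomisation. Its test is a paired one, for which 18 people per group are said to be enough. The target is stated in these words: the chosen number "would detect a within-subject mean improvement of 0.14 logits on the Activity Inventory (primary outcome) following telerehabilitation". The other inputs are an SD of the differences of 0.17 logits, 80% power and a 5% type I error. The two groups are not the trial arms. They are "two equal sized groups based on visual acuity (VA); i.e., those better or worse than 20/63". No start or end point is given for the improvement.

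Statistics and Data Analysis obtains effect sizes for basic LVR, in-office LVR and telerehabilitation by setting each follow-up score against the score before LVR. For the Activity Inventory, an explicit test between the arms appears only as the fallback for non-normal data: a responder comparison by chi-square test and logistic regression.

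**The concern.** The aim is framed around randomisation, but the trial is sized on a single-arm before-and-after change. The meaning of that change depends on its starting point, and the sections do not agree. Specific Aims implies that the post-randomisation period starts at month 1. The data-analysis text starts from the score before LVR. The sample-size text is silent.

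Neither starting point isolates telerehabilitation. What is at stake is the effect size handed to the next trial: a within-arm change taken as the telerehabilitation effect could be too large or too small, and nothing in that analysis would reveal which.

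**Working it through.** **1. The plan's own figure.** Inputs from the Sample Size calculation: mean change 0.14 logits, SD of differences 0.17, power 0.80, "0.05 type I error probability". Sidedness is not stated, so I take it as two-sided.

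- Standardised effect: 0.14/0.17 = 0.824.
- Normal approximation: n = (1.960 + 0.842)² × (0.17/0.14)² = 11.6, so 12.
- Noncentral t: n = 14 per acuity group.

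The stated 18 is not reproduced from these inputs. It would follow from power 0.90, or from 14 inflated for an unstated 20% dropout (14/0.8 = 17.5). With 18, power is 0.91. The mismatch is on the safe side and does not affect this point.

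**2. What each possible change contains.**

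| Change in the telerehabilitation arm | What it contains |
|---|---|
| Before LVR to month 4 | New device, basic LVR session, telerehabilitation, four months of device use, repeat interviewing, disease course |
| Month 1 to month 4 | Telerehabilitation, three further months of device use, a third interview, disease course |
| Run-in: before LVR to month 1 | New device, basic LVR session, one month of device use, a second interview, disease course |

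The run-in cannot be subtracted from the second row to leave telerehabilitation. It lasts one month rather than three, precedes randomisation, and contains the first effect of the device and the basic session.

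**3. The randomised contrast.** Changes over time that both arms share cancel in the difference between arms. Inputs: "We will aim to enroll a total of ~40 subjects randomized to telerehabilitation (given our 2:1 randomization plan"), about 20 in-office, and an assumed SD of change of 0.17 in both arms (the plan gives it only for telerehabilitation).

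- SE = 0.17 × √(1/40 + 1/20) = 0.0466.
- 95% CI half-width = t(58) × SE = 2.002 × 0.0466 = 0.093 logits.
- Power (two-sided 0.05, noncentral t): 0.84 for a difference of 0.14, 0.56 for 0.10 and 0.18 for 0.05.
- Within one acuity group (20 versus 10), power for 0.14 is 0.54.
- If the SD of change were 0.24 instead, power for 0.14 at 40 versus 20 would be 0.55.

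**4. Illustration only: how the paired test responds to drift.** The documents give no drift figure. I assume 0.01 to 0.03 logits per month in either direction, so 0.03 to 0.09 over three months. SD is 0.17, two-sided 0.05.

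| Upward drift, no training effect | P(significant), n = 18 | n = 20 | n = 40 |
|---|---|---|---|
| 0.03 | 0.11 | 0.12 | 0.19 |
| 0.06 | 0.29 | 0.32 | 0.59 |
| 0.09 | 0.56 | 0.61 | 0.90 |

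The plan sizes the test by acuity group, so the columns for 18 and 20 are the relevant ones; 40 is the whole arm pooled. In the other direction, a true gain of 0.14 offset by a decline of 0.03 leaves 0.11, and power at n = 18 falls from 0.91 to 0.73. A decline of 0.09 leaves 0.05, and power falls to 0.22.

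**The case against.** The strongest defence is that this is an exploratory phase 1/2 trial. Its stated primary goal is to refine methods, its analysis opens with descriptive statistics and effect sizes, and no success rule hangs on the paired test. Background and Significance calls a phase III trial premature and envisages the eventual trial as telerehabilitation against in-office LVR, possibly for equivalence. Research Design and Methods gives reasons for rejecting usual care: variable practice, the Hawthorne effect and sample size. All of this stands and limits the consequence. It does not make a within-arm change interpretable, and possible enhancement of visual function is itself listed among the unknowns the study is to address.

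A reader might infer that the trial as a whole cannot show that telerehabilitation adds anything. The documents do not support that. There is a concurrent randomised comparator on the same visit schedule, the plan allows a difference in either direction, and an advantage over in-office LVR would be controlled evidence. The limit applies to the paired test.

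A reader might also take the powered change to be month 1 to month 4. That is an inference from the two-period design; the data-analysis text points to the score before LVR.

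Nor do the drift figures estimate this trial's error rate. The drift is assumed, and disease progression could push scores down. Regression to the mean is less clear-cut: the design text describes no selection on a low Activity Inventory score.

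**Conclusion.** The concern holds for the powered analysis. The paired test cannot, on its own, attribute a gain to telerehabilitation, whichever starting score is used. From the score before LVR, the change includes the device and basic LVR. From month 1, it is still confounded with time and repeat measurement. The direction of bias is unknown.

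The trial already plans to collect the data for a sound comparison. If the SD of change is 0.17 in both arms and about 40 and 20 participants contribute, the between-arm difference is estimated to within about ±0.093 logits, two-thirds of the 0.14 target (0.093/0.14 = 0.66). That is useful for planning but too wide to rule out modest differences. It answers how telerehabilitation compares with in-office LVR. Similar gains in both arms, which the plan regards as possible, would not show that further training helped in either.

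**What to change.** 1. Reconcile Specific Aims, the data-analysis text and the Sample Size calculation so that the post-randomisation change runs from month 1 to month 4.
2. Name the telerehabilitation minus in-office difference in that change, with its 95% CI, as the main effect estimate carried forward to the future RCT, not only as the fallback for non-normal data. State its expected precision and the SD assumed for each arm.
3. Continue to report within-arm changes, labelled uncontrolled and descriptive. State that neither a larger change in the second period than in the first, nor similar gains in both arms, will be read as proof that extra training helped.
4. Restate the aim as gain with telerehabilitation relative to in-office LVR, after basic LVR.

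The cost is wording and a revised analysis statement; no new participants, visits or data are needed. The trial gives up a stand-alone claim of telerehabilitation efficacy, which this design could not support.
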